HRP-503B – BIOMEDICAL RESEARCH PROTOCOL (2017-1)

Protocol Title: Neurocomputational Models of Auditory Hallucinations

Principal Investigator: [name]

Version Date: 07/31/19

Clinicaltrials.gov Registration #: NCT04210557

SECTION I: RESEARCH PLAN

1. **Statement of Purpose:** *State the scientific aim(s) of the study, or the hypotheses to be tested.*

Hallucinations are percepts without stimulus. 70% of patients with schizophrenia suffer distressing auditory hallucinations. Their mere presence increases the risk of suicide (1-3). Most reach remission with D₂ dopamine receptor blocking drugs after 1 year of adherence. However, 30% of patients have intractable hallucinations, and 50% are non-adherent to their medications, commonly because of unfavorable side-effects – those intractable and non-adherent patients continue to suffer. There is a clear need for a mechanistic understanding of hallucinations as a prelude to rational treatment design. This proposal outlines the initial steps towards the development of an interventional biomarker for clinical hallucinations, grounded in computational neuroscience.

Computational psychiatry involves harnessing the power of computational neuroscience to address the clinical needs of those suffering from serious mental illnesses. There has been much discussion of the promise of the approach. There have been few studies thus far and they have largely involved correlative methods like functional neuroimaging. We propose to address this shortcoming by causally manipulating the neural loci of computational model parameters in-person in patients with psychosis using transcranial magnetic stimulation (TMS), tracking the impact of this manipulation on behavioral performance and model parameters. With such a causal intervention, the veracity of the model's explanation of hallucinations will be either validated or disconfirmed. If validated, the model can be further developed as a biomarker for predicting the hallucination onset, guiding, developing or tracking the effects of treatments for hallucinations. If disconfirmed, the model ought to be discarded and other alternatives should be pursued.

Rather than relying wholly upon sensory inputs, perception blends inputs with prior beliefs(4, 5). Our preliminary data show hallucinations involve an over-weighting of priors – relying too much on previous experiences rather than current sensory inputs, which we measure using a **Conditioned Hallucinations** task. Participants experience repeated pairings of visual and auditory stimuli and subsequently perceive the auditory stimulus when none is presented (*a conditioned hallucination*). We administered the task to participants with psychosis both with (P+H+) and without (P+H-) hallucinations, otherwise healthy voice-hearers (P-H+), and healthy controls (P-H-). Conditioned hallucinations were significantly more frequent in those who hallucinate (P+H+, P-H+). We employed a computational approach that yields quantitative estimates of participant-specific reliance on priors: The Hierarchical Gaussian Filter (HGF). Prior weighting – leaning more heavily on experiences earlier in the task - was increased in people with clinical and non-clinical *hallucinations* (P+H+ and P-H+; 'prior over-weighting') corresponding to **insula** responses measured with functional neuroimaging during conditioned hallucination events. In contrast, people with *psychosis* (P+H+ and P+H-, with and without hallucinations) exhibited deficits in updating their beliefs about audio-visual associations ('decreased updating 'being able to change decisions in light

Neurocomputational Models of Auditory Hallucinations

of the changing association between the light and the tone), associated with a dearth of activity in the cerebellum. In sum, there are two correlates of conditioned hallucinations in clinical voice hearers (P+H+): (1) **insula** mediated *prior over-weighting*, and (2) *Decreased updating* via a dearth of **cerebellar** engagement. We will test the importance of each correlate to the genesis of conditioned hallucinations with a specific aim:

Aim 1: To interrogate prior-overweighting with sham-controlled inhibitory TMS to the insula. We will recruit 30 clinical voice hearers (P+H+). They will complete two parallel forms of the conditioned hallucinations task (with different visual and auditory stimuli) on two occasions, separated by a week. TMS and sham will be delivered in a randomized counterbalanced order. **Hypothesis:** *Inhibiting the insula will decrease prior over-weighting.* If this computational perturbation is responsible for conditioned hallucinations, then ameliorating it with TMS that decreases insula engagement will decrease conditioned hallucination responses. Furthermore, the prior weighting parameter will be reduced following active TMS compared with sham.

Aim 2: To interrogate poor belief-updating with sham-controlled excitatory TMS to the cerebellum. We will recruit a further 70 clinical voice hearers. Again, they will complete parallel forms of the conditioned hallucinations task on two occasions, separated by a week. They will receive excitatory TMS over the cerebellum (and sham on the other occasion, in a randomized counterbalanced order). **Hypotheses:** *Exciting the cerebellum will increase belief-updating.* If poor *belief-updating* contributes to conditioned hallucinations, increasing cerebellum engagement should decrease conditioned hallucinations and alter the *belief-updating* model parameter compared with sham TMS.

We propose hypothetico-deductive tests of the computationally derived predictions from our preliminary work. Disconfirming the model would militate against its further development. Validating the model will provide grounds for developing novel interventions that address *prior-overweighting* and/or *belief-updating* in those who suffer from intractable hallucinations and who are at risk of poor outcomes including suicide.

2. **Probable Duration of Project:** *State the expected duration of the project, including all follow-up and data analysis activities.*

2 years for data acquisition and analysis (year1: aim 1, year 2: aim 2),
 1 year for publication and application for R01 level funding
 We anticipate completing data collection by July 2022

3. **Background:** *Describe the background information that led to the plan for this project. Provide references to support the expectation of obtaining useful scientific data.*

Auditory verbal hallucinations (AVH) are among the most distressing and disabling aspects of psychotic illness. They increase the risk of suicide(1-3), and are only 70% likely to respond to antipsychotics. A deeper understanding of the mechanisms underlying hallucinations and how they might relate to psychotic illness is required for the identification of psychosis-specific biomarkers and AVH-specific treatments. Computational modeling of perceptual processes offers one approach to identifying aspects of information processing that might be specific to hallucinations and others that might be specific to psychosis. Our recent work has provided such a computational understanding (6). **Here we propose to directly test this understanding (6, 7) using a causal intervention; the modulation of neural activity and thereby mental function using transcranial magnetic stimulation (TMS).**

Perception is not simply the passive reception of inputs (8). We actively infer the causes of our sensations (9). These inferences are influenced by our prior experiences (10). Priors and inputs are combined according to Bayes' rule (11). Prediction errors, the mismatch between priors and inputs, contribute to belief updating (12).

Neurocomputational Models of Auditory Hallucinations

Hallucinations (percepts without external stimulus) may arise when strong priors cause a percept in the absence of input (13). We recently tested this theory by engendering new priors about auditory stimuli in human observers using Pavlovian conditioning. Even in healthy individuals, the repeated co-occurrence of visual and auditory stimuli can induce auditory hallucinations (14). We examined this effect with functional imaging. We used computational modeling to infer the strength of participants' perceptual beliefs;

We propose two specific aims, each addressing a particular aspect of our previous work on strong priors, using a sham-controlled TMS intervention prior to behavioral testing with our conditioned hallucinations task. Aim 1 will address the role of the insula in conditioned hallucinations. Our preliminary work suggests that the insula is hyper-engaged during conditioned hallucinations and as such, we propose to use 1 Hz inhibitory TMS to decrease insula engagement and curtail the belief that tones are predicted by visual stimuli in the task. Aim 2 will address the role of the cerebellum in psychosis. Our preliminary work suggests that the cerebellum is hypo-engaged during conditioned hallucinations in patients with psychosis. We propose to use theta-burst TMS over cerebellum to increase its activity and encourage belief updating.

The dependent variables will be conditioned hallucinations as well as computational model parameters [which capture participants' task beliefs and their tendency to weight their priors over oncoming sensory evidence (Fig. 2)].

[figure not shown]

Figure 2. Hierarchical Gaussian Filter Analysis. **a.** A perceptual model is constructed, consisting of a perceptual model in which sensory input and three levels of perceptual belief are combined and fed into a response model, which determines participant responses. Of interest for this proposal are parameter v , signifying the relative weights with which perceptual beliefs are combined with sensory input, and parameter X_3 , signifying how much the belief that the light predicts the tone changes over the course of the experiment. This model was fit to individual behavioral data from each participant, and when inverted was capable of re-creating individual behavioral performance (data not shown). **b.** The change in X_3 ("change sensitivity") is significantly lower in those with psychosis compared to those without. **c-e.** Both of these measures correlate with symptom scores in the form of PANSS total score (**d**) and Launay-Slade Hallucination Scale-Revised Score (**e**). Error bars and shading represent 1 SEM. *, $p < 0.05$; ***, $p < 0.001$.

Neurocomputational Models of Auditory Hallucinations

Importantly, our model captured how priors are combined with sensory evidence, allowing us to directly test the strong prior hypothesis. First, we determined individual thresholds for detection and psychometric curves (16). Next, participants worked to detect a 1-kHz tone occurring concurrently with presentation of a checkerboard visual stimulus. At the start of conditioning, the tone was presented frequently at threshold (Fig. 1a, left), engendering a belief in audio-visual association. This belief was then tested (Fig. 1a, right) with increasingly frequent sub-threshold and target-absent trials. *Conditioned hallucinations* occurred when participants reported tones that were not presented, conditional upon the visual stimulus. We recruited four groups of participants (Fig. 1b): people with a diagnosed psychotic illness who heard voices (P+H+, n=15); those with similar who did not hear voices (P+H-, n=14); an active control group who heard daily voices, but did not have a diagnosed illness(17) (P-H+, n=15; they attributed their experiences metaphysically (18)); and finally, controls without diagnosis or voices (P-H-, n=15).

After learning the association between the visual and auditory stimuli, all groups reported hearing tones that had not been presented (**conditioned hallucinations**), although the H+ groups did so significantly more frequently (Fig 1c). Conditioned hallucinations activated a network of regions previously identified during symptom-capture based approaches to auditory hallucinations (e.g., bilateral anterior insula, association auditory cortex, inferior frontal gyrus, temporo-parietal junction, and thalamus) (19).

To understand these results in the context of our formal model of perception, we employed a three-tiered Hierarchical Gaussian Filter (HGF)(20, 21), which uses participant responses and the task structure to model estimate perceptual beliefs across three levels of abstraction (Fig. 2a). The first level of the model (X_1) represents whether the participant believes that a tone was present or not on each trial. The second level (X_2) is their belief that visual cues predict tones. The third level (X_3) is the change in belief about the contingency between visual and auditory stimuli (i.e., volatility of X_2).

HGF modeling of conditioned hallucinations in our four groups (P+H+, P-H+, P+H-, P-H-) resulted in two findings critical to the present proposal:

- 1) Those with **hallucinations** demonstrate higher degrees of perceptual belief on the first two layers (**X_1 and X_2**) and an over-reliance on prior beliefs ('**prior over-weighting**' p<0.001. Figure. 2c (6));
- 2) Those with **psychosis**, regardless of whether they hallucinate or not, are **less likely to detect changes in the statistical structure of the task (X_3)** compared to non-psychotic participants ('**change insensitivity**', p<0.05 Fig. 2b(6)). Furthermore, there was a significant negative correlation between change sensitivity and illness burden (Figure. 2d (6)) and a significant positive correlation between prior weighting and hallucination severity score (Figure. 2e (6)). Finally, we combined model parameters with the imaging data: the hierarchical levels of

[figure not shown]

Figure 3. HGF imaging results. (a) HGF trajectories for X_1 (blue) and X_3 (red) regressed onto BOLD time courses for the conditioned hallucinations task, superimposed on conditioned hallucinations network (yellow). Regions with activity covarying with X_3 included cerebellum and parahippocampal gyrus (top); activity in anterior insula and superior temporal sulcus (STS) tracked with X_1 perceptual belief trajectories (bottom). (b and c) Parameter estimates of X_1 (b) and X_3 (c) fits extracted from regions highlighted in a. Activity in cerebellum (b) differentiated those with psychosis from those without, whereas activity in insula (c) and STS (not shown) differentiated hallucinators from non-hallucinators.

Neurocomputational Models of Auditory Hallucinations

representation were mediated by different brain circuits and those circuits dissociated voice hearers from those who did not hear voices (X_1 /Insula), and patients with psychosis from people without psychosis (regardless of voice status, X_3 /cerebellum; **Figure. 3**, this effect was also significant in the hippocampus). Patients were less able to update a belief about task volatility than high APS participants. This updating correlated with responses in the hippocampus and cerebellum (22, 23). *Our preliminary results bode well for the computational dissection of hallucination mediating neural circuits using TMS that we propose. Namely to decrease insula (Aim 1) and increase cerebellar activity (Aim 2) and track the effects on conditioned hallucinations and model parameters.*

[figure not shown]

Figure 4. Symptom and cognitive effects of rTMS. 4 weeks of daily TMS significantly reduced hallucinations and symptoms more generally. Furthermore, TMS significantly improved cognition

Transcranial magnetic stimulation (TMS) is a focal, non-invasive form of brain stimulation that can depolarize or hyperpolarize superficial cortical neurons in the human brain(24). Hoffman and colleagues published the first double-blind crossover study showing that 1 Hz inhibitory stimulation of the left temporo-parietal junction (TPJ) reduced auditory verbal hallucinations (AVH, voice hearing) (25). We have delivered bilateral inhibitory 1Hz TMS over the superior temporal gyrus (960 pulses daily, 5 days a week for 4 weeks) to patients (n=15) with intractable AVH. TMS significantly improved hallucinations as well as verbal cognitive function (**Figure. 4**).

Furthermore, these improvements were associated with increases in functional connectivity between the STG and insula as well as global connectivity increases in the cerebellum. Taken together, our behavioral, imaging, computational, TMS and clinical data suggest that decreasing insula activity and increasing cerebellar activity may contribute to the therapeutic response to TMS.

We propose to test whether these neural systems implement the specific computational model-derived behaviors highlighted by our recent work. We will decrease insula activity in patients with AVH and track the effects on conditioned hallucination behavior and model parameters (Aim 1). Furthermore, we will increase cerebellar responses in another independent sample of patients with AVH and track its effects on conditioned hallucination behavior and model parameters (Aim 2). In both cases, stimulation will be compared to a sham intervention.

4. Research Plan:

Abbreviations –

Clinical Assessment Interview for Negative Symptoms (CAINS(26)); Complete blood count (CBC) Comprehensive Metabolic Panel (CMP); Electrocardiogram (EKG); Human chorionic gonadotropin (hCG) Launay–Slade Hallucination Scale (LSHS); Measurement and Treatment Research to Improve Cognition in Schizophrenia (MATRICS); Positive and Negative Syndrome Scale (PANSS); Peters Delusions Inventory (PDI); Structured Clinical Interview for DSM-5 (SCID-5); Urine Toxicology (Utox)

Measures		Pre-screen Phone Screen	Screen Visit 1	Active TMS Visit 2, 3, or 4	Sham TMS Visit 2, 3, or 4	Control TMS Visit 2, 3, or 4
Clinical Assessments	CAINS(26)					
	PANSS					
	SCID					
Physiology Analysis	CBC					
	CMP					
	EKG					
	Hearing Assessment					
	Physical Examination					
	Utox					
	Urine HCG					
Self-report	Demographics					
	LSHS					
	Medical History					
	PDI					
	Phone Screening Questionnaire					
	TMS Safety Questionnaire					
Neuro-	MATRICS Battery					

Overall Strategy: Voice hearing patient participants with a diagnosis of schizophrenia or schizoaffective disorder (confirmed by SCID-5 interview at screening) will undergo one screening interview/assessment (1 hour) and three TMS behavioral sessions during each of which participants will perform the Conditioned Hallucinations task (40 mins). On one they will receive active TMS (of insula, n=30, or cerebellum, n=70, see power calculations below). On the other two they will receive sham stimulations prior to task performance (stimulations will be delivered in a randomized counterbalanced order). Participants will be compensated \$200 for participation (\$50 per visit). All study visits will take place at the Connecticut Mental Health Center (CMHC).

Phone Screen - telephone screen that delivers study information and assesses broad eligibility via conversation (confirms that the person hears voices, that they are between 18 and 45, that they do not have a pacemaker or suffer from seizures)

Screening (at CMHC): Yale has specialty clinics for first episode and multi-episode patients that will serve as primary recruitment sources. [name] works closely with these clinics and will facilitate recruitment.

Participants will read the consent form and provide informed consent before any screening procedures commence.

Diagnosis will be established according to DSM-5 criteria using information from a SCID interview, review of medical records, and collateral informants. Participants will be between the ages of 18-45. Exclusion of older participants is based on concern for effects of aging on behavioral responses and TMS effects. Participants of both sexes and any race/ethnicity will be recruited to ensure the sample approximates the racial/ethnic base-rates in New Haven.

Self-report Measures:

- AVH – In order to recruit a sample enriched for AVH, all patient volunteers will need to report AVH at least once a day.

Clinical Assessment Measures:

- PANSS – We will use the Positive & Negative Syndrome Scale (PANSS) to confirm presence and severity of hallucinations (score of > 3 for inclusion).
- CAINS(26) – We will use the Clinical Assessment Interview for Negative Symptoms (CAINS (26)) to assess negative symptoms. The samples recruited for Aims 1 and 2 will be matched on these measures.
- LSHS – The LSHS will be administered, providing a brief measure of quasi-hallucinatory experience.
- PDI – The PDI will also be used to measure delusional ideation including measures of distress, preoccupations, and conviction associated with delusions.

A licensed clinician ([name]) will conduct or review the responses to the surveys and will be able to identify suicidality signs and take appropriate action as necessary.

As appropriate we will:

- Refer for immediate follow-up with a primary therapist (if engaged in treatment)
- Refer to a crisis line and provide the number (National Suicide Prevention Lifeline, [name])
- Refer to a walk-in community mental health clinic accompanied by another adult
- Refer to an emergency room accompanied by another adult
- Refer to an emergency room and research staff contacts emergency services

Neurocomputational Models of Auditory Hallucinations

Physiological Analysis:

- Blood Draw – We will have a CMHC phlebotomist perform a blood draw. We will draw no more than 30ml or about two tablespoons of blood. We will run routine lab work (CBC and CMP). Abnormal levels of sodium in the blood (hyponatremia and hypernatremia) is related to increased seizure risk. Therefore, we will exclude individuals with sodium levels outside of normal parameters (135 – 145 milliequivalents per liter). Abnormal CBC can indicate overall health and identify underlying conditions, therefore, participants with abnormal CBC level will be excluded.
- Urine Screen – A urine hCG and utox test will be performed. We will also be excluding participants that have a positive pregnancy test (urine hCG) and/or positive utox results.
- EKG – A EKG will be performed in order to exclude individuals with abnormal results, potentially indicating cardiac conditions.

Standard Neuropsychological Measures:

- MATRICS Battery – We will administer the MATRICS Battery to assess level of neuropsychological functioning. The samples recruited for Aims 1 and 2 will be matched on these measures and individual scores will be used as covariates in our key within-participant comparisons of TMS versus sham.

Hearing Assessment:

- Hearing Test – During the screening assessment, all participants will also undergo a hearing testing. Participants meeting criteria for mild hearing loss or greater (> 25 dB loss in the frequencies tested) will be excluded.

General TMS Procedure (at CMHC):

- rMT – Before receiving magnetic stimulation, participants will undergo a test to decide the strength of the stimulation. This will be done by using the electromagnet to stimulate a part of the brain that controls finger movement while monitoring muscle contractions with recording electrodes (similar to the ones used for the EKG) placed on your right thumb and, index finger. The amount of magnetic stimulation needed to produce slight muscle contractions will guide us in determining the level of magnetic stimulation to the part of the brain that may produce voices. A Magstim Rapid² system (Magstim Ltd, Whitland, Wales) will be used to assess resting motor threshold (rMT) and to administer TMS. For rMT, single pulses will be administered with an intensity and location so their finger twitches (abductor pollicis brevis contracts) 50% of the time (27).
- EKG – An EKG will be performed before and after TMS to indicate if the cerebellum was stimulated.

Sham Stimulation (sham TMS): This procedure involves a TMS coil with a hidden aluminum plate inside which prevents the magnetic field from stimulating the participant's brain. An eSham system will mimic the scalp feel of TMS. This system has been previously employed successfully and safely (28). There is no compelling evidence to suggest that alternating current from a TENS units or similar device modulates cortical activity. Whilst TMS is safe and highly tolerable, all screening and TMS sessions will be supervised by [name], MD, PhD.

Behavioral Task: These experiments will require repeated performance of the Conditioned Hallucinations task and re-estimation of model parameters. The task is a simple video game wherein we first ascertain the participant's threshold for detection of a 1KHz tone in white noise (the tone loud enough that they detect it 50% of the time). We then infer their 75% and 25% detection thresholds from their behavioral choices. Next, we pair tones of those intensities with the presentation of a chequerboard stimulus, such that presentation of the tones is conditional on the chequerboards. On each trial, the participants are asked to indicate whether they heard a tone and how confident they are in their choice. By arranging for the contingencies to change over time we can track how

Neurocomputational Models of Auditory Hallucinations

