TMS target engagement: In the absence of neuroimaging, it is difficult to confirm that we have engaged target regions. For each aim, we propose a brief test, post-TMS, as a positive control. The anterior insula regulates sympathetic and parasympathetic outflow and thus impacts heart rate variability (HRV)(39). For Aim 1, we propose to measure HRV before TMS administration and afterwards. Patients with psychosis who hallucinate have high HRV(40). If we engage the insula with TMS, HRV should decrease. For Aim 2, we are aiming to increase cerebellar function. Patients with psychosis tend also to have poor cerebellar motor control indexed by peg-board performance(41). Cerebellar TMS improves pegboard performance(42). We propose to measure motor ability before and after TMS administration to confirm that we have stimulated the cerebellum.

Repeated Measures: Although sensory conditioning experiments date back to the first half of the 20th century, there are few studies on these phenomena that include repeated measures. The ones that do suggest high test-retest reliability (43). The data in **Figure 5** suggest reliability of both the phenomenon and the computational model parameters we plan to test. Additionally, we will employ parallel stimulus sets.

Behavioral Variability: The model parameters of interest may be sensitive to inattention, level of arousal, and other task demands. The model assays this explicitly (β , **Fig. 2a**).

Medication: While it might be ideal to recruit un-medicated patients, the representative positive symptom patient is medicated; therefore, studies of medicated patients are more generalizable. To address medication effects, we will convert current medications into equivalents and use these as covariates in our analyses.

5. Genetic Testing N/A

A. Describe

- i. the types of future research to be conducted using the materials, specifying if immortalization of cell lines, whole exome or genome sequencing, genome wide association studies, or animal studies are planned
- ii. the plan for the collection of material or the conditions under which material will be received
- iii. the types of information about the donor/individual contributors that will be entered into a database
- iv. the methods to uphold confidentiality

B. What are the conditions or procedures for sharing of materials and/or distributing for future research projects?

Neurocomputational Models of Auditory Hallucinations

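### The target-engagement check is described inconsistently for the cerebellum and read from before/after change with no stated sham contrast, so peg-board practice can pass as engagement

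*Combined protocol and SAP*

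**What the plan says.** In the combined protocol and SAP, Section I item 4, the General TMS Procedure lists an EKG among the steps common to both aims: "An EKG will be performed before and after TMS to indicate if the cerebellum was stimulated". It mentions neither the insula nor the peg-board.

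Under Potential Problems & Alternative Strategies, the paragraph on TMS target engagement maps the measures differently and gives reasons. It concedes that "In the absence of neuroimaging, it is difficult to confirm that we have engaged target regions" and offers a short test in each aim as a positive control. HRV is linked to the anterior insula: "For Aim 1, we propose to measure HRV before TMS administration and afterwards", with the expectation that "If we engage the insula with TMS, HRV should decrease". For the cerebellum, the paragraph cites improved peg-board performance after cerebellar TMS and says "We propose to measure motor ability before and after TMS administration to confirm that we have stimulated the cerebellum". It gives no test, threshold or sham contrast for either measure.

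The planned active-versus-sham comparisons (Analyses in item 4, and item 13, Statistical Considerations) cover only the parameters of the Hierarchical Gaussian Filter. The schedule of measures has a column headed "Sham TMS Visit 2, 3, or 4", and its EKG row has boxes at the active, sham and control visits. No peg-board row can be seen, but the table breaks off in the available text.

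On the consequence of a negative finding, the Statement of Purpose says "If disconfirmed, the model ought to be discarded and other alternatives should be pursued", with no condition that the target was engaged.

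**The concern.** A null effect of TMS on the model parameters has two explanations: the model is wrong, or the stimulation did not reach its target. The second is a real possibility. The protocol calls both sites deep, places the insula coil at a fixed 6 cm from the motor spot, and navigates to the cerebellum on an average brain image, not the participant's own. Without imaging, the engagement check is the only evidence that can tell the two explanations apart.

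That check has two faults. First, the protocol gives two accounts of what shows cerebellar stimulation, and the one in the general procedure conflicts with the one that carries a rationale. Second, change over a session also reflects rest, arousal, elapsed time and, for the peg-board, practice. Without a sham contrast, such change can count as engagement that did not occur, or hide engagement that did. At stake is whether a missed target could be read as failure of the model, which the Statement of Purpose would then set aside.

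**Working it through.** **1. The two places side by side**

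| Place | Insula (Aim 1) | Cerebellum (Aim 2) |
|---|---|---|
| General TMS Procedure | none named | EKG before and after |
| TMS target engagement | HRV before and after, decrease expected | peg-board before and after, improvement expected |

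The conflict lies in one sentence. The second row assigns each measure to a site and gives a reason.

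**2. The plan's own figures**

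The plan states no sample size or power for the check, so the primary figures serve as a test of the method. For a paired t-test, two-sided 0.05, power is P(|T| > t_crit), where T is noncentral t with n − 1 degrees of freedom and noncentrality d√n.

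- Aim 1: d = 0.6, n = 24, noncentrality 0.6 × √24 = 2.94, power 80.4%.
- Aim 2: d = 0.36, n = 63, noncentrality 0.36 × √63 = 2.86, power 80.3%.

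Both stated sample sizes reproduce.

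**3. Peg-board, before/after on the active visit alone**

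Assume no engagement and a practice gain of δ SD of the change score. The documents give no peg-board variability, so δ is an assumption, shown from 0.2 to 0.4. The chance of a significant improvement uses the same formula with noncentrality δ√n; the opposite tail is negligible.

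| δ | n = 63: noncentrality, result | n = 70: noncentrality, result |
|---|---|---|
| 0.2 | 1.59, 35% | 1.67, 38% |
| 0.3 | 2.38, 65% | 2.51, 70% |
| 0.4 | 3.17, 88% | 3.35, 91% |

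**4. The same situation with an active-minus-sham contrast**

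With a true effect e and practice δ at both visits, the mean contrast is (e + δ) − δ = e. With e = 0 the two-sided rejection rate is 5% whatever δ is. The condition is that the average practice gain is the same under active and sham. Randomised, counterbalanced visit order supports this but does not guarantee it.

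**5. What the contrast costs**

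If the two changes have equal SD and correlation ρ, the contrast has SD √(2(1 − ρ)) times that of one change, so its standardised effect is e/√(2(1 − ρ)). The effect sizes below are borrowed from the primary parameters for illustration.

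| Case | Before/after alone | ρ = 0 | ρ = 0.25 | ρ = 0.5 | ρ = 0.75 |
|---|---|---|---|---|---|
| e = 0.6, n = 30 | 89% | 61% | 74% | 89% | 99% |
| e = 0.36, n = 63 | 80% | 51% | 63% | 80% | 98% |

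Break-even is at ρ = 0.5, where 2(1 − ρ) = 1.

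**6. HRV**

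The stated sign of engagement is a decrease. Downward drift would mimic it and upward drift would mask it. The documents do not say which to expect, so no false-positive rate is derived.

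**The case against.** The strongest reply has five parts.

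- **The site error is one sentence.** The paragraph that sets out the check pairs each measure with a site and a reason. This stands: it is an inconsistency, not a check mis-assigned throughout.
- **Silence is not exclusion.** The documents speak of TMS at sham visits too, so before and after TMS may well include sham, and the EKG is scheduled there. An active-minus-sham HRV change is probably obtainable. The peg-board cannot be called absent from the sham visit, since the schedule breaks off. This also stands. What remains is that the stated criterion is before/after change and the stated sham contrasts do not include these measures.
- **The arithmetic does not carry over to Aim 1.** A reader might apply the peg-board calculation to HRV and infer false engagement in 16% to 47% of trials at n=24 for drift of 0.2 to 0.4 SD. The documents do not support that: it would need downward drift. If HRV drifted upward by that much, a significant decrease would occur in under 0.2% of trials.
- **The contrast may be weaker.** Correct whenever the two changes correlate below 0.5. Used as a gate, a weaker check could make a genuine disconfirmation uninterpretable. This shapes the fix but does not rescue before/after change, whose extra power comes with the practice bias.
- **The plan already has safeguards.** The check is called a positive control, the sentence on discarding the model is a statement of purpose and not an analysis rule, each aim has a third visit with a different stimulation pattern at the same site, and Aim 2 uses neuronavigation. These lower the stakes. None says how the check is to be analysed or how it bears on a null result.

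**Conclusion.** The concern holds in a limited form. The General TMS Procedure and the target-engagement paragraph contradict each other on what indicates cerebellar stimulation. The stated criterion for engagement is before/after change, with no sham contrast.

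For the peg-board this has a known direction: practice counts towards engagement. At an assumed gain of 0.2 to 0.4 SD of change, false indication runs from about 35% to 88% at n=63 and 38% to 91% at n=70, against 5% for the contrast. These figures rest on the assumed gain, on a t-test that the plan does not specify for this check, and on equal average practice at both visits. For HRV the conclusion is qualitative only.

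A reader might go further and infer that the design cannot distinguish a wrong model from a missed target. The documents do not support this: the EKG is scheduled at sham, and peg-board data at sham cannot be ruled out. The gap is in the stated analysis and its interpretation, not shown to be in the data collected. It affects how a null result is read, and leaves the primary test and sample size untouched.

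**What to change.** 1. Amend the EKG sentence in the General TMS Procedure so that it agrees with the target-engagement paragraph: HRV for Aim 1, peg-board for Aim 2.
2. Define engagement in each aim as the active-minus-sham difference in post-minus-pre change, in the same participants. Confirm that HRV and the peg-board are recorded before and after stimulation at the sham visit, and that the schedule shows both.
3. Report this estimate with a confidence interval beside the primary result. Because the contrast can have less power than before/after change, do not use it as a pass/fail gate.
4. Qualify the Statement of Purpose: a null primary result without evidence of engagement is not by itself taken as disconfirming the model.

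The cost is mostly wording, settled before unblinding. If the peg-board is not already planned at the Aim 2 sham visit, it adds a few minutes there. No extra visits or participants are needed. The statistical price is the possible loss of power for the check, for example 61% to 74% against 89% at n=30 for a 0.6 SD effect when the two changes correlate 0 to 0.25.
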